2.2.2. Safety Endpoints

- Incidence, nature, and severity of AEs and serious adverse events (SAEs)
- Incidence of AEs leading to KZR-616 discontinuation
- Changes in standard laboratory parameters and vital signs

2.2.3. Exploratory Endpoints

- Relationships between clinical efficacy, clinical safety, and various biomarker endpoints including changes in circulating cytokine and whole blood gene expression
- Corticosteroid-free TIS response by visit (corticosteroid-free is defined as corticosteroid fully tapered off for ≥ 12 weeks [3 months] prior to a visit; minimal response = TIS ≥ 20 , moderate response = TIS ≥ 40 , major response = TIS ≥ 60)

3. STUDY DESIGN

3.1. Type and Design of Study

This is an open-label study to evaluate the long-term efficacy and safety of KZR-616 in patients with active PM or DM who completed the double-blind treatment period of Study KZR-616-003, up to and including the Week 32 Visit, prior to the first dose of open-label KZR-616.

The study design schema is presented in [Figure 1](#).

Patients will be evaluated for eligibility according to the entry criteria (see [Section 4](#)) at, or within 8 weeks after, the Week 32 Visit (ie, the End of Treatment [EOT] Visit [Visit 34]) of Study KZR-616-003. Informed consent may be signed prior to the Week 32 Visit of Study KZR-616-003, and must be signed prior to any study-related activity in KZR-616-003E. For patients who are eligible and willing to enroll in the open-label extension study, the KZR-616-003 Week 32 Visit may also serve as Visit 1 (Day 1) for the open-label extension study. Assessments at this visit performed as part of Study KZR-616-003 will be used as baseline values for the extension study; therefore, these assessments must be performed prior to the first dose of open-label KZR-616 (see [Figure 1](#)).

[figure not shown]
All patients will receive a SC injection of 30 mg KZR-616 at Visit 1 (Day 1), followed by weekly SC injections of 45 mg KZR-616 up to a maximum of 96 weeks. Study drug administration will end for all patients in Study KZR-616-003E when the last patient enrolled has completed 48 weeks of dosing. Patients will have a final follow-up visit 12 weeks after their last dose of KZR-616 (End of Study [EOS] Visit), for a maximum potential length of participation of 108 weeks.

On-site study visits will occur at Weeks 12, 24, 36, 48, 60, 72, 84, and 96 (EOT Visit), and the EOS Visit. At these visits, safety and efficacy assessments will be performed according to the Schedule of Assessments ([Table 1](#)). While these visits are mandatory, in recognition of constraints imposed by the SARS-CoV-2 pandemic, sites may elect to use a combination of telemedicine (as permitted by their institutions) and/or home health providers, including at-home administration of KZR-616. All other study visits may occur either at the site or at patients' homes via home health providers ([Table 2](#)). If necessary, samples for clinical laboratory assessments will be collected by home health providers and sent to the laboratory. For at-home KZR-616 administration, doses may be administered by home health providers or, for patients deemed appropriate by the Investigator, by the patient or caregiver following appropriate instruction (see [Section 5.4](#)).

Efficacy assessments will be performed for all patients, unless indicated otherwise; these assessments are discussed in [Section 7.2.4](#).

Safety will be assessed throughout the study by monitoring of vital signs, clinical laboratory tests, and physical examinations, and by recording and analyzing all AEs and SAEs.

Figure 1 Study KZR-616-003E Study Design Schema

- a Informed consent may be signed at any time relative to step 2; however, it must be signed prior to steps 3 and 4.
- b Values used as baseline values for KZR-616-003E
- c The first dose (Day 1) will be 30 mg KZR-616 SC; subsequent doses will be 45 mg KZR-616 SC.

Abbreviations: I/E=inclusion/exclusion; SC=subcutaneous

3.1.1. Study Design Rationale

This is an open-label, up to 108-week study to evaluate the long-term efficacy and safety of KZR-616 in patients with PM or DM who completed the double-blind treatment period of Study KZR-616-003 (ie, up to and including the Week 32 Visit prior to the first dose of open-label KZR-616).

3.2. Minimization of Bias

KZR-616-003E is an open-label study.

3.3. Number of Sites

Up to 24 sites are planned to participate in this study.

4. PATIENT SELECTION AND ENROLLMENT

4.1. Number of Patients

Up to 24 patients are planned for enrollment.

Patients will be evaluated for eligibility in the open-label extension study according to the eligibility criteria (see [Section 4](#)) at, or within 8 weeks after, the Week 32 Visit of Study KZR-616-003. The Investigator will ensure that the patient has provided written informed consent before administration of open-label KZR-616 as part of the open-label extension study KZR-616-003E.

Once informed consent is obtained, the evaluations may begin to assess study eligibility (inclusion/exclusion criteria). The patient identification number used in Study KZR-616-003 will continue to be used to identify the patient throughout study participation.

4.2. Inclusion Criteria

Only individuals who meet all of the following criteria may be enrolled in the study.

1. Must have successfully completed Study KZR-616-003 through Week 32, including the Week 32 Visit assessments, be willing and able to provide written informed consent prior to any study-related procedures, and be willing and able to comply with study requirements.
2. Women of childbearing potential (WOCBP) must have a negative urine or serum pregnancy test prior to the first dose of KZR-616 in KZR-616-003E, and must agree to continue to use a highly effective method of birth control until completion of the study (or 30 days following the last dose of KZR-616 in case of early withdrawal). Women of childbearing potential are defined as postpubescent female patients, unless the patient is postmenopausal (defined by amenorrhea for at least 2 years or amenorrhea for at least 1 year with confirmatory follicle stimulating hormone [FSH] level in the postmenopausal range, as documented historically or measured by the central or local laboratory and if patient is not on supplementary hormonal therapy) or surgically sterile (ie, tubal ligation, hysterectomy, bilateral salpingoophorectomy). See [Section 7.2.8](#) for detailed requirements for WOCBP.
3. Male patients must continue to use an effective contraception method (eg, condom with spermicide) for 1 week following their last dose of KZR-616 or be congenitally or surgically sterile (eg, vasectomy with documented confirmation of post-surgical aspermia).

4.3. Exclusion Criteria

Only individuals who do not meet any of the following criteria may be enrolled in the study.

1. Have clinical evidence of significant unstable or uncontrolled diseases other than the disease under study (eg, cardiac [including congestive heart failure, hypertension, angina,

or myocardial infarction], pulmonary [including pulmonary hypertension or interstitial lung disease], hematologic, gastrointestinal, endocrinologic, hepatic, renal, neurological, or infectious disease, any ongoing SAE(s), or AE(s) \geq Grade 3 by National Cancer Institute Common Terminology Criteria for Adverse Events [NCI-CTCAE]) that, in the opinion of the Investigator or Sponsor/designee, could confound the results of the study, put the patient at undue risk, or interfere with protocol adherence.

2. Has participated in any clinical study other than KZR-616-003 between the Week 32 Visit of Study KZR-616-003 and the first study visit of KZR-616-003E, if they are not on the same calendar day.
3. Are females who are breastfeeding or who plan to become pregnant during the study, or who are actively trying to conceive at the time of signing of the informed consent form (ICF).
4. Have hypersensitivity to KZR-616 or any of its excipients.

5. STUDY TREATMENT INFORMATION

Instructions for the receipt, inspection, storage, preparation, administration, and disposal of KZR-616 will be provided in a separate Pharmacy Manual at each clinical site.

5.1. Physical Description of KZR-616

KZR-616 is supplied as a refrigerated lyophilized drug product in single use borosilicate glass vials. Each vial is reconstituted with sterile water for injection prior to administration.

5.2. Packaging and Labeling

The lyophilized drug product will be supplied in single-use vials packaged in multi-vial cartons. For patients eligible for at-home administration by the patient or caregiver, a premeasured, pre-filled syringe (PFS) containing sterile water for injection (WFI), a needleless vial adaptor system, and additional clinical supplies needed for reconstitution will also be provided. All KZR-616 vials and pre-filled syringes will be labeled according to appropriate regulatory guidelines. All packaging and labeling operations will be performed according to Good Manufacturing Practice (GMP) for Medicinal Products and the relevant regulatory requirements.

5.3. Supply, Dispensing, Storage, and KZR-616 Accountability

Refer to the Investigator's Brochure and Pharmacy Manual for storage conditions for KZR-616.

The Investigator or designee must confirm appropriate temperature conditions have been maintained during transit for all KZR-616 received and any discrepancies are reported and resolved before use of the KZR-616.

Only participants enrolled in the study may receive KZR-616. All investigational products should be stored in an environmentally controlled and monitored (manual or automated) area in accordance with the labeled storage conditions. Access to investigational product must be limited to the Investigator and authorized site staff.

The Investigator, institution, or the head of the medical institution (where applicable) is responsible for study treatment accountability, reconciliation, and record maintenance (such as receipt, reconciliation and final disposition records).

Upon receipt of the KZR-616, the Investigator (or designee) will conduct an inventory of the supplies and verify that KZR-616 supplies are received intact and in the correct amounts. The Study Monitor may check the study supplies at each study center at any time during the study.

It is the responsibility of the Study Monitor to ensure that the Investigator (or designee) has correctly documented the amount of the KZR-616 received, dispensed, and returned on the dispensing log that will be provided. A full drug accountability log will be maintained at the study center at all times. The Study Monitor will perform an inventory of KZR-616 at the closeout visit to the study center. All discrepancies must be accounted for and documented.

5.4. At-Home Administration of KZR-616 by Patient or Caregiver

KZR-616 for at-home administration by the patient or caregiver may be dispensed as described in the Pharmacy Manual.

The site will assess patients' willingness and ability to undergo at-home administration of KZR-616. Patients considered for at-home administration must:

- be willing to self-administer (including administration by caregiver) KZR-616, and
- have been assessed as appropriate for at-home administration by the Investigator (eg, demonstrated tolerability to KZR-616, physically and mentally able).

Patients or caregivers may administer KZR-616 SC after appropriate instruction.

Patients and caregivers will be provided specific Instructions for Use (IFU) to ensure proper handling, storing, reconstitution, administration, and disposal of KZR-616. The IFU will be accompanied by an instructional video demonstrating each step involved.

Patients will document details of dates, times, and volumes of each administered dose in a patient diary. Patients will be instructed to return all used vials of drug product to the investigational site.

Patients who do not wish to administer KZR-616 at home will have the option of having KZR-616 administered at the site or by a home health provider.

6. DOSAGE AND KZR-616 ADMINISTRATION

6.1. KZR-616 Administration

KZR-616 will be administered by SC injection once weekly. The first injection will be a 30-mg dose, administered at the study site, and subsequent injections will be a 45-mg dose. Ideally, the first dose will be given on the same calendar day as the Week 32 Visit of Study KZR-616-003, but must be given no later than 8 weeks after the Week 32 Visit of Study KZR-616-003.

After the first dose, KZR-616 will be administered by study personnel at the site or by a home health provider at the patient's home. At-home administration of KZR-616 by the patient or caregiver may also be available as an option, as appropriate (see [Section 5.4](#)). Doses will be administered according to the Schedules of Assessments ([Table 1](#) and [Table 2](#)).

Further details regarding drug product formulation, preparation, and administration of KZR-616 will be provided in a separate Pharmacy Manual.

6.1.1. Administration Site

Subcutaneous injection sites should be rotated (eg, 4 abdominal quadrants, posterior upper arms, anterior thighs), and a minimum of 4 weeks should separate injections to the same anatomic site, if possible.

6.1.2. Suggested Measures to Improve KZR-616 Tolerance

Initial SC doses of 60 mg KZR-616 are associated with at least one of the following signs/symptoms: hypotension, tachycardia, nausea, vomiting, dizziness, headache, pyrexia, rigors and/or chills. These signs/symptoms typically begin within 8 to 24 hours after dosing, and usually resolve within 48 hours after dosing.

Although the numbers are small, the percentage of patient reporting treatment-emergent AEs (TEAEs) of the above signs/symptoms appears to be lower in patients who received KZR-616 as step-up doses and/or with pre-/post-dose prophylaxis, suggesting that these methods are effective at tolerizing patients to higher doses of KZR-616.

Step-up Dosing

It is unknown whether patients who start, stop, and then resume treatment with KZR-616 will experience tolerability issues (eg, patients randomized to Arm A of Study KZR-616-003). Thus, to maintain the blind for Study KZR-616-003, all patients enrolling in Study KZR-616-003E will receive an initial dose of 30 mg KZR-616, to be followed weekly by the target dose of 45 mg.

Pre/Post Dose Prophylaxis

Prophylactic measures may be considered if any of the signs and/or symptoms listed above develop, and may be used as treatment, either while the patient is at the study site or after leaving the study site. Measures that have been demonstrated to reduce the incidence and severity of infusion-related reactions with other proteasome inhibitors include the following:

- Fluid hydration, eg, 250-500 mL oral (or intravenous [IV] if necessary) of an electrolyte solution up to 48 hours prior to dosing, or up to 24 hours after dosing if symptoms are present

- Antiemetics, non-sedating antihistamines, and/or acetaminophen (if fever is present)

If additional guidance for improving initial tolerability symptoms is required, the Medical Monitor should be consulted. Home health providers do not provide or administer any of the fluids or medications listed above.

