1. INTRODUCTION

Study KZR-616-003E is an open-label extension of the Phase 2 study KZR-616-003, which is a randomized, double-blind, placebo-controlled crossover study to evaluate the efficacy and safety of KZR-616 in the treatment of patients with active polymyositis (PM) or dermatomyositis (DM).

1.1. 26S Proteasome Background

The 26S proteasome is a ubiquitously expressed protein complex responsible for the homeostatic control of protein turnover and regulated degradation of proteins involved in most cellular functions (Ciechanover 2012; Coux 1996; Wilk 1983). Each proteasome contains a 20S core, containing 2 copies of 3 distinct proteolytic enzymes, and 2 regulatory caps forming a 26S complex.

The proteasome exists in 2 forms: the constitutive proteasome and the immunoproteasome. The constitutive proteasome is expressed ubiquitously throughout the body and is responsible for protein degradation in tissues such as the heart, kidney, and liver. In the constitutive proteasome, proteolytic activities are encoded in the β 5, β 1, and β 2 subunits and are characterized based on substrate specificity as chymotrypsin-like (CT-L), caspase-like (C-L) and trypsin-like (T-L), respectively. The immunoproteasome is expressed primarily in hematopoietic cells (eg, lymphocytes and monocytes), and is induced in cytokine-exposed nonhematopoietic cells (Glynne 1991; Martinez 1991; Nandi 1996). In the immunoproteasome, low-molecular mass polypeptide (LMP) 7, LMP2, and multicatalytic endopeptidase complex-like 1 (MECL-1) replace the β 5, β 1, and β 2 subunits of the constitutive proteasome, respectively. Low-molecular mass polypeptide 7 has a similar substrate preference as β 5 and is thus referred to as the CT-L subunit of the immunoproteasome.

The proteasome has been validated as a therapeutic drug target through regulatory approval of 3 compounds, bortezomib (VELCADE[®]), carfilzomib (KYPROLIS[®]), and ixazomib (NINLARO[®]), for use in the treatment of the plasma cell neoplasm, multiple myeloma. These compounds all show equivalent potency for the β 5 subunit of the constitutive proteasome and the LMP7 subunit of the immunoproteasome (Kirk 2012; Kisselev 2012). This dual-targeting nature is necessary for their ability to induce cytotoxicity in multiple myeloma cells and other cell types. Selective inhibitors of LMP7 or β 5 alone have no cytotoxic potential (Parlati 2009).

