9.1.6. Documentation and Reporting of Adverse Events

Adverse events (including SAEs) should be reported and documented in accordance with the procedures outlined below. All AEs occurring during the study must be documented on the relevant eCRF pages. The following data should be documented for each AE.

- Diagnosis, or description of the symptoms if a diagnosis is not established
- Classification of 'serious' or 'not serious'
- Severity
- Date of first occurrence and date of resolution (if applicable)
- Action taken with regard to KZR-616
- Outcome of the event (unknown, recovered, not yet recovered, recovered with sequelae, death [with date and cause reported])

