9.5.1.1. Tolerability Symptom Complex

Initial SC doses of 60 mg KZR-616 are associated with a complex of tolerability symptoms, with at least one of the following signs or symptoms: hypotension, tachycardia, nausea, vomiting, dizziness, headache, pyrexia, rigors, and/or chills. These symptoms typically begin within 8 to 24 hours after dosing, and usually resolve within 48 hours of dosing. These signs and symptoms can occur with any dose, though they are more likely to occur with initial doses of 60 mg or higher. When seen, they tend to be more common with the first dose than with subsequent doses.

The complex of tolerability symptoms seen with initial high doses of KZR-616 are similar to those seen with infusion reactions reported for carfilzomib ([KYPROLIS 2018](#)), as well as with systemic inflammatory response syndrome, a clinical syndrome that is a subset of cytokine

release syndrome manifested by at least 2 of the following findings: tachycardia (>90 beats per minute), leukocytosis ($>12 \times 10^9/L$ or $<4 \times 10^9/L$, or $>10\%$ immature [band] forms), tachypnea (respiratory rate of more than 20 breaths per minute or arterial carbon dioxide tension [PaCO₂] of less than 32 mmHg), and fever (temperature of more than 38°C [100.4°F] or less than 36°C [96.8°F]) (Bone 1992). The relative roles of the immunoproteasome versus constitutive proteasomes to these specific events are not known.

In reporting TEAEs related to KZR-616 tolerability, terms such as the NCI-CTCAE terms of ‘infusion-related reaction,’ ‘cytokine release syndrome,’ ‘acute infusion reaction,’ or ‘allergic or hypersensitivity reaction’ should not be used. Instead, each sign or symptom should be recorded as an individual TEAE. If multiple signs or symptoms occur with a given systemic injection-related event, each sign or symptom should be recorded separately with its own level of severity.

Management of these symptoms is described in [Section 6.1.2](#).

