10. STATISTICAL ANALYSES

This study is descriptive in nature, and no formal hypothesis testing will be performed. No formal statistical sample size estimation has been performed, since the number of patients in this study is determined by the number of patients who completed Study KZR-616-003 and enrolled in this study. Descriptive statistics, including the numbers and percentages for categorical variables; and the numbers, means, standard deviations (SD), medians, minimums and maximums for continuous variables will be provided by treatment group, by indication (DM, PM), and overall.

The number and percentage of patients who experience TEAEs, SAEs/death, AEs leading to treatment/study discontinuation, and treatment modification/delay due to AE(s) will be summarized by treatment group and overall. The number and percentage of patients experiencing any TEAE(s), overall, and by system organ class (SOC) and preferred term and by grade will be tabulated.

Continuous measures in laboratory, vital sign, ECG, and efficacy data will be summarized descriptively (mean, median, SD, and minimum and maximum values) by treatment group and overall and will be summarized by protocol-specified time point along with a summary of change from baseline at each time point. Changes in physical examinations will be listed for each patient and described. In addition, 95% confidence intervals may be provided to describe some continuous efficacy data.

Patient listings will be provided to support these summaries.

PK analyses will include determination of plasma levels of KZR-616 including C_{max} , T_{max} , and AUC.

Full Analysis Set (FAS): The FAS for summaries of efficacy endpoints will include all patients who receive KZR-616 in this study and have baseline and any post-baseline data. All observed data will be included in the statistical summaries. No missing data will be imputed except as pre-defined in the SAP.

Per Protocol (PP): A PP population may be used to analyze select efficacy endpoints, and will be based on KZR-616 exposure (time on treatment) and protocol deviations. The decision to summarize a PP population will be made prior to database lock.

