Safety Population: The safety population will include all patients enrolled who received at least one dose of KZR-616, and will be the population used for the analysis of safety. Adverse event data will be coded to system organ class and preferred term using Medical Dictionary for Regulatory Activities (MedDRA; Version 19.1 or later).

Data will be summarized for the following groups of patients based on the sequence of treatments received in Study KZR-616-003:

Group 1: Arm A (KZR-616:Placebo) from Study KZR-616-003 beginning on Day 1 (first dose of KZR-616) through the end of Study KZR-616-003E

Group 2: Arm B (Placebo:KZR-616) from Study KZR-616-003 beginning on Week 16 (first dose of KZR-616) through the end of Study KZR-616-003E

Groups 1 and 2 combined: from the first dose of KZR-616 in KZR-616-003 through the end of KZR-616-003E

Group 3: Arm B2: Patients receiving KZR-616 from Weeks 16-32 in KZR-616-003 followed by KZR-616 in OLE throughout KZR-616-003E, to evaluate patients who continuously received KZR-616 from KZR-616-003 through KZR-616-003E

Groups 1 and 2 are being assessed for any differences due to the intervening placebo treatment period in Group 1. The rationale for combining Group 1 and Group 2 is to encompass all KZR-616 treatment, and the rationale for assessing Group 3 is to encompass all continuous KZR-616 treatment.

Further details of the statistical methodology, including methods for handling missing data and early withdrawals, will be provided in an SAP that will be finalized prior to database lock. As KZR-616-003E is an open-label extension study, endpoints in addition to those described in [Section 2.2](#) may be conducted as described in the final SAP.

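### The adverse event windows in Section 10 dilute and confound any acute reaction to restarting KZR-616, a question the protocol itself leaves open

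*Combined protocol and SAP*

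**What the plan says.** Section 6.1.2 (Step-up Dosing) leaves restart tolerability open: "It is unknown whether patients who start, stop, and then resume treatment with KZR-616 will experience tolerability issues". It then gives everyone the same first extension dose: "Thus, to maintain the blind for Study KZR-616-003, all patients enrolling in Study KZR-616-003E will receive an initial dose of 30 mg KZR-616". The parent trial is described in Section 1 as one "which is a randomized, double-blind, placebo-controlled crossover study".

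Section 10 summarises treatment-emergent events, serious events and events leading to discontinuation or modification as numbers and percentages of patients, by treatment group and overall. Nothing is split by period or by time since a dose. The groups are defined by parent-study sequence. The first reads "Group 1: Arm A (KZR-616:Placebo) from Study KZR-616-003 beginning on Day 1 (first dose of KZR-616" and continues to the end of the extension. Group 2 is Arm B from Week 16 of the parent study, its first KZR-616 dose, to the same end. Group 3, the continuously treated Arm B patients, also starts at Week 16. Section 10 gives the purpose of setting Group 1 beside Group 2 as finding differences due to the intervening placebo period.

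On timing, Section 9.5.1.1 says of the tolerability complex: "These symptoms typically begin within 8 to 24 hours after dosing, and usually resolve within 48 hours of dosing". It adds that the signs are commoner with the first dose than with later ones, and that each sign is to be recorded as its own event. Section 9.5.1 makes the complex an adverse event of special interest. Section 10 describes no summary of it.

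**The concern.** The reaction of interest lasts a day or two, but the planned summaries cover one and a half to nearly three years. Three features work against seeing it.

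- The first-ever dose, when these signs are commonest, lies inside both groups' windows. A patient who had a headache then is already counted, so a headache at restart adds nothing to the patient count.
- Headache, nausea, dizziness and fever also arise for other reasons, and the count fills up over a long extension.
- As worded, Group 1 includes 16 weeks on placebo that have no counterpart in Group 2. Group 1 can therefore show more events with no restart effect at all.

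The planned Group 1 against Group 2 comparison could thus miss a real restart reaction or suggest one that is not there. The question also reaches beyond Arm A, because Sections 6.1.3.2 and 8.1.2 allow dosing to resume after an interruption.

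**Working it through.** The plan states no event rate, power or sample-size figure on this point, so there is none to reproduce. Every event rate below is an assumption.

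**Window lengths** (Sections 3.1 and 10: 32-week parent study with Arm B's first dose at Week 16; up to 96 weeks of extension dosing; 12 weeks of follow-up; any entry gap is extra)
- Group 1: 32 + 96 + 12 = 140 weeks. Group 2: 16 + 96 + 12 = 124 weeks. Difference: 16 weeks.
- With 48 weeks of extension dosing: 92 and 76 weeks.
- The first 4 extension weeks are 4/140 = 2.9% of Group 1's window (4/92 = 4.3% in the shorter case).

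**Dilution by background.** Let r be the rate of first occurrence of any sign per patient-year, w the weeks on drug (16 + 48 = 64 or 16 + 96 = 112), and 0.30 the added chance of a restart reaction.
- Without a restart effect: b = 1 − exp(−r × w × 7/365.25).
- With it: c = 1 − (1 − b)(1 − 0.30).
- Difference: c − b = 0.30 × exp(−r × w × 7/365.25).

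| r per year | 64 weeks | 112 weeks |
|---|---|---|
| 0.5 | 0.30 × 0.542 = 16 points | 0.30 × 0.342 = 10 points |
| 1 | 0.30 × 0.293 = 8.8 points | 0.30 × 0.117 = 3.5 points |

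**Dilution by the first-ever start.** A second model, assuming independence, takes 30% of restarters and 5% of continuers with a sign, a true difference of 25 points.
- Pooling in a 30% first-start rate: 1 − 0.7 × 0.7 = 51% against 1 − 0.7 × 0.95 = 33.5%, a difference of 17.5 points.
- Adding a 50% background: 1 − 0.7 × 0.7 × 0.5 = 75.5% against 1 − 0.7 × 0.95 × 0.5 = 66.75%, a difference of 8.8 points.
- Over first-start rates of 10 to 50% and backgrounds of 0 to 70%, the pooled difference runs from about 4 to 22.5 points.

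**Unequal length with no restart effect.** Using 1 − exp(−r × weeks × 7/365.25) over the whole window:
- r = 1: 93.2% against 90.7% (140 v 124 weeks), 2.5 points; 82.9% against 76.7% (92 v 76 weeks), 6.2 points.
- r = 0.5: 73.9% against 69.5%, 4.3 points; 58.6% against 51.7%, 6.9 points.

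This spurious excess is of similar size to some of the diluted true effects.

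**What a short window can deliver.** Section 4.1 says: "Up to 24 patients are planned for enrollment". The allocation ratio is not given; 1:1 is assumed, so about 12 per arm.
- A short window keeps the full 25 points for 30% v 5%, but the power of a two-sided 5% Fisher test is only 16% at 12 v 12 and 7% at 9 v 9.
- Power near 80% at 12 v 12 needs about 60% v 5% (78%) or 70% v 10% (83%).
- An observed 4/12 v 1/12 gives a 95% interval (Newcombe) of about −8 to +53 points.
- An observed 0/12 gives an exact two-sided 95% upper limit of 26%.

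**The case against.** The strongest reply is that the protocol already recognises the contrast. Section 10 says that Groups 1 and 2 are compared for the effect of the placebo period, promises patient listings, and leaves further methods to an SAP finalised before database lock. That is fair: the data are recoverable and the table can still be added. It does not remove the point, because the windows Section 10 does specify do not serve the purpose it gives for them.

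A reader might infer that this randomised contrast would answer the restart question. It would not. Section 10 says: "This study is descriptive in nature, and no formal hypothesis testing will be performed", and about 12 per arm can show only a very large effect. Nor is the comparison fully randomised. Section 4.2 admits only patients who completed the parent study through Week 32, and those patients must then choose to enrol. Section 6.1 allows up to 8 weeks before the first extension dose, so some Arm B patients also interrupt and restart. Optional prophylaxis under Section 6.1.2 could differ between arms.

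A reader might also infer from Section 9.1.6, which lists "Date of first occurrence and date of resolution (if applicable", that onset times are not recorded and that the form needs new fields. That list cannot be the whole record, since it omits the causality assessment required by Section 9.1.3, and the case report form is not in the documents. A date-based table does not need clock times in any case. Recording each sign separately is no obstacle either, because an any-sign count can be derived from it.

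Finally, Section 10 tabulates any event, system organ class and preferred term, not a nine-sign composite. For a single preferred term the background would be lower and the proportional dilution smaller, although the restart effect on one term would be smaller too.

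**Conclusion.** The point holds as a mismatch between a stated purpose and the chosen windows. Following Section 10 as written gives an adverse event comparison that is diluted by first-start and background events and confounded by 16 weeks of unequal follow-up, on a question that Section 6.1.2 raises. Under the assumed 30% restart effect and background of 0.5 to 1 per patient-year, between about one half (16 of 30 points) and one ninth (3.5 of 30 points) of the effect would remain. It would be too strong to say that the effect vanishes: 16 and 10 points remain at the lower background rate, and the second model gives up to 22.5 of 25. The size depends on unsourced rates, but the direction does not. A short-window table would be a descriptive estimate. It would be conditional on completing the parent study and enrolling, and informative only about restarting under the step-up common to all patients.

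**What to change.** Add to Section 10 or the SAP, before database lock, one descriptive table by parent-study arm:

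- The number and percentage of patients, each counted once, with any of the nine Section 9.5.1.1 signs starting on the dosing day or the next 2 days, separately for the first and second extension doses. Section 6.1.3.2 requires at least 4 days between doses, so these windows cannot overlap.
- Exact 95% confidence intervals for each arm, and the Arm A minus Arm B difference with its interval.
- The length of the gap since the Week 32 Visit, and a repeat of the table in patients who rolled over on the same day.
- A note that the table is descriptive, with about 12 per arm if allocation was 1:1, can show only a very large effect, and is conditional on completing Study KZR-616-003 and enrolling.

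The cost is one table and its repeat. It uses adverse event and dosing dates, so it requires no new case report form fields, and it implies no change to dosing. The downside is wide intervals, widest in the same-day subset. Fixing the window in advance avoids choosing it after the events have been seen.
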